STUDY PROTOCOL AND STATISTICAL ANALYSIS PLAN

Official title: Feasibility and effectiveness of real-time, remote continuous glucose monitoring in adolescents with poorly controlled type 1 diabetes

NCT number: NCT04540536

IRB Approved Document date: 05-08-23

Study Title

Feasibility and effectiveness of real-time, remote continuous glucose monitoring in adolescents with poorly controlled type 1 diabetes

Background

Achieving optimal glycemic control in patients with Type 1 diabetes mellitus (T1D) is a challenge, especially in the adolescent population; the T1D exchange registry revealed that the mean hemoglobin A1c was 9.3% between ages 15-18, higher than the ADA target of <7.5%.¹ Poor glycemic control increases risk for acute diabetes complications including diabetic ketoacidosis (DKA) and increases risk for long-term complications including nephropathy, neuropathy, retinopathy, and macrovascular disease.²

The demands on the adolescent for self-care are arduous: the American Diabetes Association (ADA) recommended standards of care for youth (children and adolescents) with type 1 diabetes include frequent blood glucose checks (up to 6-10 times daily) and an intensive insulin regimen (either via basal insulin and multiple daily injections of prandial insulin or via continuous subcutaneous insulin infusion).³

Barriers to glycemic control in patients with T1D include premature transition in responsibility for managing diabetes from parents to teens, risk taking behaviors among adolescents, lack of feeling of peer normalcy, fatigue from diabetes care, and varying insulin requirements owing to physiological pubertal changes requiring frequent dose changes.⁴

Continuous glucose monitors (CGM) measure interstitial fluid glucose readings on a real-time continuous basis. Previous studies have shown the clinical benefit of CGM in reducing hemoglobin A1C (HbA1c) with regular use of the device among patients with diabetes requiring insulin. Two devices are currently approved by the Food and Drug Association (FDA) to be used for insulin dosing. The Dexcom G6 CGM does not require scheduled calibration and has the added features of customizing alarms for hyperglycemia and hypoglycemia, which could help facilitate appropriate changes in insulin therapy. This technology also allows real-time blood glucose values to be transmitted remotely to other devices.⁵

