Many parents of patients with type 1 diabetes are not appropriately involved in their care, as both neglectful and intrusive supervision can lead to poor diabetes control.⁶ This raises the question of a potential role for clinicians in supervising and guiding diabetes management directly to patients with uncontrolled diabetes. To our knowledge, there are no published studies describing direct monitoring and oversight of CGM by medical professionals in an outpatient setting. A recent retrospective analysis of 15,000 children aged 2-18 years who used Dexcom CGM revealed that 94.8% had the “share” function enabled, which allows primary caregivers to follow glucose readings⁷. We plan to assess the efficacy, safety, utility and acceptability of 3 months of CGM use in adolescents with poorly controlled T1D under free-living conditions, with our clinic staff directly following blood glucose levels in real-time, and communicating reciprocally with patients and parents regarding actionable abnormalities in blood glucose levels.

Study Protocol

Study Hypothesis

A three-month real-time, remote continuous glucose monitoring period with two-way text messaging between healthcare providers, patients, and parents improves hemoglobin A1c in adolescents with poorly controlled type 1 diabetes.

Overview of methodology

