We plan to conduct an open-label, single-center, single-arm three-period study. We aim to recruit 25 adolescents aged 13-18 years with poorly controlled T1D as evidenced by Hemoglobin A1c \geq 12% or a 30% annual risk of developing DKA in the following year according to a predictive model developed at our institution. At a threshold value of probability of admission \geq 0.3 (95% specificity) our model can identify a high-risk subset of approximately 8% of the patients who collectively have a 40% probability of admission in the 12 months following assessment.⁸ We will obtain a written informed consent from guardians and assent from study participants before any study-related activities. We will obtain each patient's demographic information, time since diagnosis, previous hospital admissions. Patient Health Questionnaire (PHQ-9A)⁹ and a point-of-care hemoglobin A1c as standard of care. We will administer a quality of life questionnaire (assessed by the Pediatric Quality Life Inventory for teens 13-18, PedsQL4.0)¹⁰, a self-efficacy and self-management questionnaire (assessed by The Self-Efficacy for Diabetes Self-Management measure (SEDM)¹⁰), and a questionnaire to assess parent-child collaboration in diabetes care (assessed by the Collaborative Parent Involvement Scale¹²).

The first phase of the study will be a surveillance phase in which a blinded Dexcom G6 will be used to obtain baseline values including time in range, percent highs, and percent lows, and percent CGM use. We will use this phase as a run-in period to reduce the chance of noncompliance with the study.

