Participants who wore the device at least 60% of the time will then proceed to the second phase of the study which aims to provide a nonblinded CGM for patient use with professional real-time monitoring. If the CGM is worn less than 60% of the time, the participant may be withdrawn from the study at the discretion of the study investigator. Participants will be encouraged to use CGM data for insulin dosing and to monitor their own blood glucose levels. Additionally, participants will share their CGM data with our clinic and with their legal guardians, utilizing the real-time share/follow Dexcom function. Clinical personnel, who could be either endocrinology fellows, endocrinology nurse practitioners or certified diabetes educators, will provide direct supervision and will communicate routinely with participants and guardians using secure text messaging (see Procedure section for more details). Remote monitoring will occur on 7 days per week between 8:00 AM and 8:00 PM. Clinical personnel will have real-time access to patient blood glucose data and will make management recommendations based on the diabetes management plan, will review insulin trends every week, will provide motivational texts to participants, and will respond to any diabetes-related concerns raised by participants. Participants

will receive \$10 gift card for every study follow-up visit completed, with a total compensation of \$30 per participant.

The third study phase will provide unblinded CGM to patients without real-time monitoring. Participants and their families will still have the ability to communicate with our clinic through routine clinically available means, mainly through the electronic patient portal and/or calling the urgent line. This study phase will be exploratory to assess whether any improvement in diabetes control after real-time monitoring continue to exist after real-time monitoring is withdrawn.

Inclusion criteria

- Age between 13-18
- Diagnosis of type 1 diabetes for at least six months.
- Both sexes and all ethnicities included.
- Subject and at least one parent able to communicate in English.
- Poorly controlled T1D as evidenced by a $\geq 30\%$ annual risk of developing DKA in the following year OR Hemoglobin A1c $\geq 12\%$
- Treated with subcutaneous insulin, either with a basal/bolus insulin regimen or a continuous subcutaneous insulin infusion (CSII) device.

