- Willing to wear CGM and utilize the share function to clinician and guardian, with measuring blood glucose checks as required by the CGM.
- Owning a smartphone compatible with Dexcom G6 software to allow the use of share/follow features with internet access capabilities
- Willing to participate in secure text messaging with study personnel.
- Female participants must have a negative pregnancy test.

Exclusion criteria

- Type 2 diabetes, secondary diabetes or CF related diabetes.
- Other severe chronic disease (e.g., cancer) which in the judgment of the investigator is likely to significantly affect glycemic control.
- Patients cannot be taking systemic corticosteroids at enrollment because of adverse effects on glycemic control, but we will not disqualify subjects who require such therapy during the study. Inhaled or topical corticosteroids are permissible.
- Patients with uncontrolled hypothyroidism (TSH >20) or uncontrolled hyperthyroidism will be excluded from the study. Patients with out of range values may be retested after medication dose adjustment.

- Developmental delay or behavioral disorder in the patient of sufficient severity, in the judgment of the investigator, to interfere with study activities. Severe uncontrolled depression defined as PHQ-9A >15 at time of enrollment is an exclusion criterion.
- Medical or psychiatric disorder in a parent of sufficient severity, in the judgment of the investigator, to interfere with study activities.
- Pregnancy, planned pregnancy or breast feeding
- CGM adhesive allergy
- Skin condition that makes CGM placement contraindicated.
- Sick cell disease or hemoglobinopathy
- Red blood cell transfusion within 3 months prior to study enrollment

Recruitment

Study team members or clinic providers can distribute flyers to patients who qualify to participate in this research study to aid in recruitment of participants. The patient recruitment flyer contains basic description of the study, including use of Dexcom G6, study timeline, brief descriptions of each visit, and compensation for participating in the study. Please see Appendix 1 for copy of the flyer.

Other forms of recruitment include distributing letters via mail and via Children's Health MyChart web portal to patients who may qualify for the study. Please see Appendix 2 for the template for the letters.

Study Timeline

Study procedures

Study design

This is a pilot study that will not include a control group. It will enroll 25 subjects.

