This will be a telephone call scheduled 10 days (+ 4 days) by a clinical research staff member to review blinded CGM data for the purpose of logging CGM parameters including average glucose with standard deviation, time in range, percent highs, percent lows, and severe lows, and days with CGM data. If the CGM is worn less than 60% of the time, the participant may be withdrawn from the study at the discretion of the study investigator. Each participant, with the help of a guardian, will insert a non-blinded sensor according to the Dexcom G6 user guide, connect the Dexcom to a compatible phone, and activate the share functions with the clinic. If the guardian is not able to set-up the Dexcom at home, the patient and guardian will be asked to come for Visit 2B within 5 days to have the non-blinded Dexcom set-up in clinic and assure that inserting the CGM is a skill that could be done independently. If the guardian or participant cannot demonstrate that they can set-up the CGM system independently, the participant will be withdrawn from the study.

Between Visit 2T and Visit 3, clinic research staff will actively monitor the participants' blood glucose levels remotely through an Apple iPad. Currently available commercial Dexcom software is able to monitor up to 10 devices on a single iPad, and we plan to have two iPads

throughout the study period. Active remote monitoring of CGM data will occur during 7 days per week between 8:00 AM and 8:00 PM.

The goal of the secure text messaging is to provide supervision and feedback to the adolescents that is supportive and collaborative, with the ultimate goals of increasing self-efficacy and improving diabetic self-management skills. The intention is not to make the texting platform cumbersome and to allow the participants freedom in making lifestyle choices that will not interfere with their diabetes control. Only reactive texts and coaching texts will be sent during the school hours.

Participants will still be able to use normal clinic communication methods through the electronic patient portal and diabetes telephone emergency line as usual. Participants will be free to optimize their treatment independently as previously educated about trend management. We will provide a letter for school indicating that the participants are a part of a study and they have to carry their cell phones with them and respond to text messaging from us.

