Collaborative Parent Involvement Scale		X		X	X

[figure not shown]

Figure 1. Timeline for study. Study visits are denoted by arrows. A timescale in months is below the timeline; there is not a specified interval between Visits 1 & 2.

Participant withdrawal criteria

The following study withdrawal criteria will apply:

1. Participants can terminate involvement in the study at any time point without any repercussions.
2. If data on the CGM is available < 60% of the time worn, patient may be withdrawn at the discretion of the research investigator.
3. If pregnancy occurs during study period.
4. Allergic reaction to adhesive surface of CGM sensor

Primary endpoint

The primary outcome is change in Hemoglobin A1c (HbA1c) between the baseline visit (Visit 2) and three-month follow-up visit (Visit 3) after active remote monitoring and secure text messaging.

A 5% significance level will be used to declare statistical significance for the primary outcome comparison.

Exploratory endpoints

- Change in Peds PHQ-9A, PED-QOL4A, SEDM, and Collaborative Parent Involvement Scale scores.
- Time taken for a text to be read by participant and guardian.
- Time spent by medical provider per participant per day.
- The difference in A1c between clinical remote monitoring HbA1c (Visit 3) and self-monitoring utilizing CGM (Visit 4)
- The difference in A1c from baseline (Visit 2) and after the two phases of the study intervention (Visit 4).
- The following outcomes will be compared between baseline, three months and six months using repeated measures ANOVA as follows:
 - Time spent in the target glucose range from 70–180 mg/dL
 - Time spent below target glucose 70 mg/dL

- Time spent above target glucose 180 mg/dL
- Average of time the participants wore the CGM

Statistical Plan

Paired sample t-tests will be used to assess continuous variable differences between two time points. Generalized linear models will be run to identify items in medical and social histories that could predict hemoglobin A1c, the primary outcome. Point estimates will be reported with 95% CIs.

As this is a pilot exploratory study, we will implement per-protocol analysis and not an intention-to-treat analysis. Only patients who have completed the three phases of the study will be included for analysis.

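### Feasibility is in the title, but no endpoint counts how many enrolled participants get through each stage, and the completers-only rule leaves the planned process measures describing only those who finished

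*Combined protocol and SAP*

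**What the plan says.** All references are to the combined protocol and SAP.

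- **Question posed.** The Study Title is "Feasibility and effectiveness of real-time, remote continuous glucose monitoring in adolescents with poorly controlled type 1 diabetes". The Background sets the aim: "We plan to assess the efficacy, safety, utility and acceptability of 3 months of CGM use in adolescents with poorly controlled T1D". Study design adds: "This is a pilot study that will not include a control group. It will enroll 25 subjects".
- **Points at which participants can leave.** Overview of methodology says of the blinded sensor phase: "We will use this phase as a run-in period to reduce the chance of noncompliance with the study". The rule on low wear, given there and again under Visit 2B or 2T, leaves the decision to the investigator: "If the CGM is worn less than 60% of the time, the participant may be withdrawn from the study at the discretion of the study". Visit 2B or 2T adds: "If the guardian or participant cannot demonstrate that they can set-up the CGM system independently, the participant will be withdrawn from the study". Participant withdrawal criteria lists own choice, pregnancy, adhesive allergy and a data-availability rule not tied to a phase: "If data on the CGM is available < 60% of the time worn, patient may be withdrawn at the discretion of the research investigator".
- **Endpoints.** The primary endpoint is HbA1c change from Visit 2 to Visit 3. The exploratory endpoints are four questionnaire scores, how long texts take to be read, daily provider time per participant, two further HbA1c contrasts, glucose time in, below and above range, and CGM wear. Safety endpoints count clinical events.
- **Analysis set.** The Statistical Plan is per-protocol: "Only patients who have completed the three phases of the study will be included for analysis".

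**The concern.** In a 25-person pilot in a high-risk group, the participants who do not manage the run-in, cannot set up the device or drop out are a large part of the feasibility result. The plan creates these exits and records them through its visits and withdrawals, but it pre-specifies no count of them.

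The analysis rule then acts on the process measures that are planned. Wear is summarised after people could be removed for low wear. A participant who finishes the whole remote-monitoring phase but misses Visit 4 loses their text-reading and provider-time data, although both belong to a phase they completed. Provider time spent on participants who later leave is not counted either. That matters for judging whether the programme can be run: the Budget puts educator time at 36 × 20 × $50 = $36,000 of a $37,300 total.

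At stake is a report of good wear and prompt text reading among completers, with no planned figure for how many of those enrolled could not be served.

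**Working it through.** **1. Stages against planned counts.**

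| Stage | What the plan does | Planned count or share of enrolled |
|---|---|---|
| Blinded run-in | At least 60% wear proceeds; below 60% may be withdrawn at discretion | None |
| Unblinded set-up and sharing (Visit 2T/2B) | Unable to set up independently: withdrawn | None |
| Remote monitoring to Visit 3 | Withdrawal criteria apply | None |
| CGM without remote monitoring to Visit 4 | Withdrawal criteria apply | None |
| Analysis | Only those finishing all three phases | Not applicable |

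Because withdrawal below 60% is discretionary, having at least 60% wear and proceeding to phase two are different events and need separate counts.

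**2. The plan's own figure.** The only sized quantity is the HbA1c comparison. Inputs are SD 1.5, change 1, alpha 0.05 (two-sided assumed) and 80% power. With 1.5 taken as the SD of the paired change:

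n = (1.5 × (1.960 + 0.842) / 1)² = 17.66, rounded up to 18.

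The stated 18 reproduces under the normal approximation. It is a power figure. Enrolling 25 leaves 25 − 18 = 7 (28%), but the documents neither link the two numbers nor state a drop-out rate.

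**3. Precision of a progression count.** The exact (Clopper-Pearson) 95% interval for x of n = 25 runs from the 0.025 quantile of Beta(x, n − x + 1) to the 0.975 quantile of Beta(x + 1, n − x). The counts below are assumptions.

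| Reaching a stage | Share | Exact 95% CI |
|---|---|---|
| 15/25 | 60% | 38.7-78.9% |
| 18/25 | 72% | 50.6-87.9% |
| 20/25 | 80% | 59.3-93.2% |
| 23/25 | 92% | 74.0-99.0% |

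**4. Effect of the completers-only rule on a process measure.** Suppose s participants start a phase, c of them finish all three phases, and the two groups' means differ by g (completers minus the rest). Then

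completer mean − mean of all starters = g × (s − c)/s.

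For run-in wear, assuming all 25 start, the multiplier is 7/25 = 0.28 if 18 finish and 10/25 = 0.40 if 15 finish. The documents give no value for g. For wear its sign is likely positive, because low wear is itself a ground for removal. For text-reading and provider time an optimistic direction is plausible but less certain.

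**The case against.** The strongest case on the other side has four parts.

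- **The plan is not silent on feasibility.** Wear, text-reading time and provider time are listed endpoints. The Visit 2B or 2T section also plans the percentage of texts in each category, and Data management plans week-by-week CGM data. A reader might infer that feasibility goes wholly unanswered; the documents do not support that. What lacks a planned figure is feasibility among all those enrolled.
- **Not every output is clearly confined to completers.** Safety endpoints lists all adverse events over the whole study, and this may include non-completers; the plan does not say. The inference that every analysis excludes those who left is therefore too strong.
- **The only stated hypothesis concerns HbA1c, and a participant flow table could still be produced.** Both are true, and no data are lost. But the title and aim pose a wider question, and the documents do not plan such a table or fix its denominator, intervals or reasons for loss.
- **Headcounts are a weak measure of acceptability.** This stands. Leaving because of pregnancy or an adhesive allergy says little about whether remote monitoring was welcome. The four questionnaires measure depression, quality of life, self-efficacy and parent involvement, so they do not measure acceptability of the programme either.

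The run-in precedes remote monitoring and Visit 4 follows it, so those two counts bear less directly on the monitored phase. They still matter, because both determine who is analysed.

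**Conclusion.** The point holds. The title and aim raise feasibility, utility and acceptability; no endpoint counts progression of enrolled participants; and the completers-only rule, read literally, restricts the planned process measures to those who finished. These measures are then likely to look too favourable as feasibility results, most clearly for wear. The HbA1c comparison can still be run, so this should be fixed but does not stop the study.

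Its size cannot be computed from the documents, which give no expected retention. If 18 to 15 of 25 finished, retention would be 72% to 60%, and the completer mean of a measure begun by all 25 would differ from the all-starter mean by 0.28 to 0.40 of the gap between those who finish and those who do not.

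A reader might take 18 of 25 as the plan's retention benchmark. It is not: 18 is the HbA1c sample size, and under the analysis rule those 18 would have to complete all three phases, not merely reach Visit 3. The conclusion rests on reading the analysis rule as applying to the exploratory process measures, which its wording does without exception.

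**What to change.** Add one paragraph to Exploratory endpoints and the Statistical Plan that exempts feasibility and process measures from the completers-only rule.

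Report the number and proportion, with all enrolled as the denominator and exact 95% CIs, who:

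1. had at least 60% blinded CGM wear and, separately, proceeded to phase two;
2. completed unblinded set-up and sharing at Visit 2T/2B;
3. reached Visit 3 still sharing data with the clinic;
4. reached Visit 4.

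Give the recorded reason for each loss. Report wear, text-reading time and provider time for everyone who starts the relevant phase; a completer-only summary can stand beside it. Describe retention as an indirect indicator of acceptability only. Do not present 18 of 25 as a target taken from the plan. State whether the adverse-event listing includes non-completers.

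The counts come from visit and withdrawal records, so no new visit or measurement is needed and no withdrawal rule changes. The cost is one paragraph and one table, wide intervals at n = 25, and feasibility results that may look less favourable.

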Schedule of procedures

Screening, Visit 1

Screening visit. It will include review of inclusion and exclusion criteria and obtaining informed consent from legal guardians and assent from participants. The visit is expected to take around one hour. The visit can be combined with Visit 2.

Participants will be recruited from either an endocrinology inpatient floor or the outpatient clinic.

Baseline, Visit 2

The visit will include review of diabetes history including current doses, prior hospitalizations, previous complications, and detailed medical and social histories and a complete physical examination that will include measurement of height and weight. A capillary blood sample will be obtained for HbA1c determination using the Alere Afinion device. A HbA1c from within two weeks of Visit 2 may also be used. A urine pregnancy test will be performed on females capable of becoming pregnant.

Participants and guardians will be introduced to the concept of a continuous glucose monitor in general, with specific details about how to apply, use, and share the Dexcom G6 data. Mandatory alarms will be set for participants and followers for blood glucose below 70 mg/dL, blood glucoses above 250 mg/dL, “urgent low soon”, “signal loss”, and “no reading” alerts. Participants may set extra alarms to personalize their diabetes alerts. Participants will also be taught to log their food and insulin intake into the CGM device.

Participants will complete the PHQ-9A, PEDS-QoL4, Self-Efficacy for Diabetes Self-Management measure (SEDM) questionnaire, and Collaborative Parent Involvement Scale. A blinded CGM will be placed on the participant with the goal to obtain baseline data for 10 days. A test secure text message will be sent through TigerConnect to guardian and participant, and they will be introduced to the messaging platform used. We will determine with the participants and parents their preferred contact hours and school hours to allow texting for non-urgent matters to be done at convenient times. This visit will take up to 2 hours.

Between Visit 2 and Visit 2T, participants and clinical staff will be notified if there is signal loss from the blinded CGM. Dexcom, Inc. will provide troubleshooting of the blinded CGM if any technical issues arise. Participants will be asked to continue taking care of their diabetes as usual and will not have access to the CGM data.

Telephone or Clinic Follow-up, Visit 2B or 2T

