- Primary language spoken at home, patient and parents' ability to converse in English if not primary

Laboratory data

- Present and past HbA1c

New clinical data will be obtained in this study. Please refer to the Table of Assessments for a list of these data.

Height and weight

Participant's heights will be measured with a properly calibrated stadiometer at times specified in the study timeline. Heights will be measured three times in immediate succession (with subjects instructed to bend and stretch between measurements) and the average used. Weight will be measured with the subject lightly clothed and without shoes. If the research visit must be performed via telemedicine visit, the participants will measure their height and weight using a measuring tape and weight scale available at their home.

Physical Examination

Physical examinations, including general appearance, head, eyes, ears, nose and throat, chest, cardiac, abdomen, extremities and neurologic and injection site examinations will be conducted at times specified in the study timeline. Any clinically significant abnormality in physical findings noted during the study should be reported as an adverse event. Any clinically significant abnormalities persisting at the end of the study will be followed by the investigator until resolution or until reaching a clinically stable endpoint. If the research visit must be performed via telemedicine visit, the physical examination will be performed as able within the telemedicine platform. This includes visual appearance of general appearance, head, eyes, nose, mouth, chest, extremities, and injection sites. Vital signs will not be able to be measured during a telemedicine visit.

Psychological and Quality of Life Assessment

PHQ-9A and PEDS-QoL4 are validated surveys will be used to screen for depression and to assess for quality of life, respectively.

Measure of self-efficacy and diabetes management

We will utilize the "Self-Efficacy for Diabetes Self-Management measure (SEDM)" questionnaire¹⁰, which is a 10-item self-report scale with good reliability (Cronbach's alpha = .90). It covers the major aspects of diabetes self-management including monitoring blood

glucose levels, dosing insulin, food choices, and exercise, and performance of diabetes-related tasks when feeling overwhelmed or frustrated. Total score range for the SEDM is 1–10.

Measure of Collaborative Parent Involvement

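### For participants who qualify by HbA1c of at least 12%, the qualifying value can also be the baseline of an uncontrolled pre-post test, so regression to the mean is counted as effect

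*Combined protocol and SAP*

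**What the plan says.** Under Inclusion criteria, poor control is shown by either of two routes: HbA1c of at least 12%, or a high predicted risk of DKA. The Overview of methodology words the second route as "or a 30% annual risk of developing DKA in the following year". The expected share of participants by each route is not given.

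Under Schedule of procedures, the Screening, Visit 1 text says "The visit can be combined with Visit 2". The Baseline, Visit 2 text schedules a capillary HbA1c and then adds "A HbA1c from within two weeks of Visit 2 may also be used". The table of assessments lists HbA1c at Visits 2, 3 and 4 and none at screening. Nothing requires the qualifying value to differ from the baseline value.

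Study design states "This is a pilot study that will not include a control group". The primary endpoint is the change in HbA1c from Visit 2 to Visit 3, judged at the 5% level. The Statistical Plan uses paired t-tests for differences between two time points, restricts analysis to participants who complete all three phases, and sizes the study at 18 for a 1% change with an SD of 1.5%. The Study Hypothesis is causal: the monitoring and messaging period improves HbA1c.

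Under Evaluations, Laboratory data, the plan collects "Present and past HbA1c". No planned analysis uses the past values to set an expected course.

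**The concern.** A value chosen because it is at or above 12% is on average higher than the same person's usual level. Part of it is short-term variation that will not recur at Visit 3. If that value is also the baseline, the expected change from Visit 2 to Visit 3 is a fall even when the intervention does nothing. The primary test compares the change with zero, so it counts this fall as effect.

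A controlled design would subtract the artefact, and here there is no control group. The 10-day blinded run-in does not help, because it repeats CGM and not HbA1c. The stated 5% error rate therefore does not apply to the claim in the Study Hypothesis. A significant primary result could be read as support for remote monitoring when part of the fall, possibly a large part, comes from how participants were selected.

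**Working it through.** **The plan's own figure.** n = ((1.96 + 0.84) × 1.5 / 1)² = 17.66, rounded up to 18. The stated sample size reproduces with the normal approximation, two-sided. Exact paired-t power is 76% at n = 18 and 89% at n = 25.

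**Inputs.**
- Entry threshold 12% (Inclusion criteria).
- Mean HbA1c 9.3% (Background). This is a registry mean for ages 15-18, used here as a proxy for the clinic.
- SD 1.5% (Statistical Plan), taken as the population SD of HbA1c.
- Normality, and a within-person correlation r between baseline and Visit 3. Both are assumptions. The documents give no r, so 0.7 to 0.9 is shown.

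**Size of the artefact by the HbA1c route.** k = (12 − 9.3)/1.5 = 1.8. The mean excess of selected values over 9.3 is 1.5 × φ(1.8)/(1 − Φ(1.8)) = 1.5 × 2.197 = 3.30, so selected participants average 9.3 + 3.30 = 12.6%. If that value is the baseline, the expected fall with no treatment effect is (1 − r) × 3.30.

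**Chance of p<0.05 with no effect.** This is the two-sided noncentral paired t with n = 18 and SD of change 1.5, as in the sample size calculation. In the half mix, half enter by HbA1c and the others are assumed not to regress, so the mean fall is halved.

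| Assumed r | Fall, all by HbA1c | Chance of p<0.05 | Fall, half mix | Chance of p<0.05 |
|---|---|---|---|---|
| 0.9 | 0.33 | 14% | 0.16 | 7% |
| 0.8 | 0.66 | 42% | 0.33 | 14% |
| 0.7 | 0.99 | 75% | 0.49 | 26% |

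At n = 25 the all-HbA1c rates are 18%, 56% and 89%.

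**Consistency of the SD.** A population SD of 1.5 and an SD of change of 1.5 hold together only at r = 0.5 in an unselected population, since 1 − 1.5²/(2 × 1.5²) = 0.5. At r = 0.9, 0.8 and 0.7 the SD of change among selected participants would be about 0.66, 0.91 and 1.08. With those values the all-HbA1c rates at n = 18 rise to about 52%, 83% and 95%. With the half mix, simulation gives about 15%, 26% and 35%. The rates in the table are therefore on the low side for the stated correlations.

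**Sensitivity to the population SD.** With an SD of 2.0 in place of 1.5, the falls by the HbA1c route are 0.36, 0.72 and 1.09 at r = 0.9, 0.8 and 0.7.

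**What re-measurement achieves.** If the baseline is a fresh value taken after qualification, the residual fall is 3.30 × (r between qualifying and baseline value − r between qualifying value and follow-up). With the follow-up correlation at 0.8, the residual is 0.00, 0.33 or 0.49 when the qualifying-to-baseline correlation is 0.80, 0.90 or 0.95. Re-use of the qualifying value gives 0.66. Re-measurement can remove all of the artefact or only part of it.

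**The case against.** The strongest reply is that the plan declares a single-arm exploratory pilot and promises point estimates with 95% confidence intervals. The lack of a control group is a stated design choice, and what remains is largely a limit on interpretation. This stands as an argument about severity. It does not remove the problem, because the plan still sets a 5% significance level, a powered sample size and a causal hypothesis for the primary outcome.

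The second reply concerns size. A reader might infer that the whole sample is selected on extreme HbA1c, and that regression to the mean would produce most of the 1% target. The documents do not support either. DKA risk is a separate route with an unknown share, and regression in those participants cannot be computed from the documents. Even with everyone entering by HbA1c, more than half of the 1% requires r below about 0.85, and at r = 0.9 the fall is a third of it. With the half mix, r must be below about 0.70. No r is given.

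A reader might also infer from "Participants will be recruited from either an endocrinology inpatient floor or the outpatient clinic" that inpatients are enrolled at a personal HbA1c peak. The documents say nothing about how HbA1c at admission relates to a patient's usual level, so no weight is put on this.

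The 9.3% mean is not this clinic's, and 1.5% is a single planning figure used here in two roles. Both objections are fair. They make the percentages illustrative. However, every case calculated gives an error rate above 5%.

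**Conclusion.** The concern holds for participants who qualify by HbA1c. Their qualifying value may be their baseline, and nothing in the plan separates regression to the mean from the effect of monitoring. Under a mean of 9.3%, an SD of 1.5, normality and r of 0.9 to 0.7, the fall with no effect is roughly 0.3 to 1.0 points in these participants. It is about 0.16 to 0.5 overall if half the sample enters by the other route and does not regress. The matching chances of a significant result at n = 18 are 14% to 75% and 7% to 26%, and higher when the SD of change is made consistent with those correlations.

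These figures do not show that an observed fall would be wholly, or even mostly, artefact. They show that the size of the artefact is unknown under the plan and could be large relative to the 1% target. Given the declared uncontrolled pilot design, this is a should-fix.

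**What to change.** 1. Delete the sentence allowing an HbA1c from within two weeks. Use the capillary HbA1c already scheduled at Visit 2 as baseline for everyone, and require the qualifying HbA1c to be a separate, earlier chart value. This removes part of the artefact, not necessarily all of it. The cost is that a qualifying value must already be on the chart, so a few same-day enrolments would be delayed.

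2. Keep the paired t-test, and pre-specify a supplementary analysis (for example a mixed model) that uses the past HbA1c values already listed for collection to compare Visit 3 with each participant's expected value. Exclude values at or soon after diagnosis: eligibility needs only six months since diagnosis, so a long look-back could reach them. Report the change from Visit 2 to Visit 3 separately by entry route. The cost is chart extraction, recording the entry route and one added model.

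3. State in the Statistical Plan that the raw p-value for the change from Visit 2 to Visit 3 does not by itself show that remote monitoring improves HbA1c. The cost is one sentence and a more modest claim.

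None of this needs a control arm or more participants.
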